Appendix 3. List of Abbreviations

Appendix 4. List of pre-specified AESIs

Table Adverse Events of Special interest				
	Medra version 24			
Category of Interest	Criteria/Programming Details			
Hemodynamic events	Arrhythmia related investigations, signs and symptoms (SMQ); Cardiac arrhythmia terms (incl bradyarrhythmias and tachyarrhythmias) (SMQ); Bradycardia; Heart rate decreased; Heart rate abnormal; Maximum heart rate decreased;Tachycardia;Heart rate increased; Maximum heart rate increased;Hypertension;Hypotension			
	Hyperfibrinogenaemia; Prothrombin level abnormal; Prothrombin level increased; Prothrombin time prolonged; Prothrombin time abnormal; Thrombocytosis; Leukocytosis; White blood cell count increased; White blood cell count abnormal;Blood fibrinogen			
	increased; Blood fibrinogen abnormal; Activated partial thromboplastin time prolonged; Activated partial thromboplastin time abnormal; Platelet count abnormal; Platelet count increased; Fibrin D dimer increased; Haptoglobin abnormal; Haptoglobin increased; Blood albumin abnormal; Protein total abnormal; Albumin globulin ratio abnormal; C-reactive protein abnormal; C-reactive protein increased; Neutrophilia; Neutrophil count abnormal;			
Inflammatory events	Lymphocytosis; Lymphocyte count abnormal; Eosinophilia; Eosinophil count abnormal; Monocytosis; Monocyte count abnormal			
	Blood thyroid stimulating hormone abnormal;Blood thyroid stimulating hormone increased;Thyroxine free abnormal;			
thyroid-related events	Thyroxine increased			

Table Adverse Events of Special Interest

PFIZER CONFIDENTIA	4L
Page 42	

Daily Sign and Symptom Collection	Entry Criterion #3 Targeted (used for study entry)	Daily Signs and Symptoms Collection	Targeted Symptom Analysis	Long Term Follow-Up
Cough	Х	Х	Х	Х
Shortness of Breath or difficulty breathing	X	Х	Х	Х
Fever	Х			Х
Feeling Feverish		Х	Х	
Chills or shivering	Х	Х	Х	Х
Fatigue (low energy or tiredness)	X	Х		X
Malaise				Х
Muscle or Body Aches	Х	Х	Х	Х
Diarrhea (loose or watery stools)	X	Х	Х	X
Nausea (feeling like you wanted to throw up)	X	Х	Х	Х
Vomiting (throw up)	Х	Х	Х	Х
Headache	Х	Х	Х	Х
Sore Throat	Х	Х	Х	Х
Stuffy or runny nose (Rhinorrhea)	X	Х	Х	Х
Loss of smell		Х		Х
Loss of taste		Х		Х
Difficulty with concentration				Х
Sleep disturbances				Х
Heart palpitations				Х
Other Symptoms				Х

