### 2.2.1. Nonclinical Studies of PF-07321332

Data from nonclinical studies support the planned clinical trials with PF-07321332; these studies are described in the IB.

PF-07321332 exhibits a broad-spectrum activity across the Coronaviridae family of 3CL proteases demonstrating its potential for antiviral efficacy.

In vitro, PF-07321332 inhibited SARS-CoV-2 viral-induced cytopathic effect in monkey kidney Vero cell assays. PF-07321332 exhibited antiviral activity against SARS-CoV-2 in dNHBE cells. Furthermore, PF-07321332 inhibited HCoV229E viral-induced cytopathic effect in human MRC-5 cells with no detectable cytotoxicity at the highest compound concentration tested.

Test article-related findings identified in the safety pharmacology studies included changes in locomotor activity and transient higher respiratory rate and minute volume in rats at the high

dose, as well as minor and transient hemodynamic changes (increased blood pressure and decreased heart rate) at the high dose in cynomolgus monkeys. The potential effects on safety pharmacology parameters are monitorable in the clinic, and no correlated clinical signs or histopathological findings in the relevant organs were observed in the 14-day or 15-day repeat dose GLP toxicity studies in rats or monkeys. ECG data were also collected in the 15-day GLP monkey study and there were no test article-related changes in ECG parameters (HR, RR-, PR-, QRS-, QT-, QTc-intervals) or ECG morphology in that study.

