## 2.3.1. Risk Assessment

Potential Risk of Clinical Significance	Summary of Data/Rationale for Risk	Mitigation Strategy
	Study Intervention(s) PF-07321332	
Emesis	Sporadic emesis was observed at ≥100 mg/kg/day of PF-07321332 in the 15-day NHP toxicology study.	AEs will be monitored and participants may receive antiemetics.
Hemodynamic and inflammatory effects	Low level inflammation (increase in fibrinogen) in 15-day NHP toxicology study and changes in platelets, globulin and albumin/globulin ratio and coagulation system (increase in PT and aPTT) in 14-day rat toxicology study.	In addition to vital signs and close observation for AEs, fibrinogen, platelets, D-dimer, PT and aPTT, albumin, and total protein will also be monitored. Refer to Section 8.3.8.
TSH elevations	TSH changes observed with the administration of	TSH and T4 (free) will be monitored.
	PF-07321332 during study C4671001	Refer to Section 8.3.8.
	Study Intervention(s): Ritonavir	
Gastrointestinal disturbances (including diarrhea, nausea, vomiting and abdominal pain)	Frequently reported adverse reaction in HIV-positive patients who are HIV-positive at 600 mg BID.	Lower dose of 100 mg twice daily is used in this study. There will be close observation of AEs. In addition to ongoing review of AEs by the sponsor, an E-DMC will review safety data as described in Section 10.1.5.1.
		Taking study intervention with food may improve tolerability.
Neurological disturbances (eg, paresthesia, including oral paresthesia, dysgeusia and	Frequently reported adverse reaction in patients who are HIV-positive at 600 mg BID.	Lower dose used in this study. There will be close observation of AEs.
dizziness)		In addition to ongoing review of AEs by the sponsor, an E-DMC will review safety data as described in Section 10.1.5.1.
Rash (most commonly reported as erythematous and maculopapular, followed by pruritic)	Frequently reported adverse reaction in patients who are HIV-positive at 600 mg BID.	Lower dose used in this study. There will be close observation of AEs and monitoring through targeted physical exams. If needed therapeutic interventions per SoC may be provided.

Potential Risk of Clinical Significance	Summary of Data/Rationale for Risk	Mitigation Strategy

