### 8.2.6. Clinical Safety Laboratory Assessments

See Appendix 2 for the list of clinical safety laboratory tests to be performed and the SoA for the timing and frequency. All protocol required laboratory assessments, as defined in Appendix 2, must be conducted in accordance with the laboratory manual and the SoA. Unscheduled clinical laboratory measurements may be obtained at any time during the study to assess any perceived safety issues.

Laboratory safety parameters will be graded according to the Division of AIDS (DAIDS) Table for Grading the Severity of Adult and Pediatric Adverse Events, version 2.1. The investigator must review the laboratory report, document this review, and record any clinically relevant changes occurring during the study in the AE section of the CRF. Clinically significant abnormal laboratory findings are those which are not associated with the underlying disease, unless judged by the investigator to be more severe than expected for the participant's condition.

All laboratory tests with values considered clinically significantly abnormal during participation in the study or within 28 days after the last dose of study intervention should be repeated until the values return to normal or baseline or are no longer considered clinically significant by the investigator or medical monitor.

If such values do not return to normal/baseline within a period of time judged reasonable by the investigator, the etiology should be identified and the sponsor notified.

See Appendix 6 for suggested actions and follow-up assessments in the event of potential drug-induced liver injury.

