### 8.3.8. Adverse Events of Special Interest

Adverse events of special interest (AESIs) are examined as part of routine safety data review procedures throughout the clinical trial and as part of signal detection processes.

AESIs include hemodynamic events, inflammatory events, and thyroid-related events.

All AESIs must be reported as an AE or SAE following the procedures described in Sections 8.3.1 through 8.3.4. An AESI is to be recorded as an AE or SAE on the CRF. In addition, an AESI that is also an SAE must be reported using the CT SAE Report Form.

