- When an AE or SAE occurs, it is the responsibility of the investigator to review all documentation (eg, hospital progress notes, laboratory reports, and diagnostic reports) related to the event.
- The investigator will then record all relevant AE or SAE information in the CRF.
- It is **not** acceptable for the investigator to send photocopies of the participant's medical records to Pfizer Safety in lieu of completion of the CT SAE Report Form/AE or SAE CRF page.
- There may be instances when copies of medical records for certain cases are requested by Pfizer Safety. In this case, all participant identifiers, with the exception of the participant number, will be redacted on the copies of the medical records before submission to Pfizer Safety.
- The investigator will attempt to establish a diagnosis of the event based on signs, symptoms, and/or other clinical information. Whenever possible, the diagnosis (not the individual signs/symptoms) will be documented as the AE or SAE.

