6.6.1. Adverse Events

All adverse events will be coded according to the Medical Dictionary for Regulatory Activities (MedDRA) and will be summarized by treatment group within SAS population. Only TEAE summaries to AEs that started on or prior to Day 34 will be summarized. A list of pre-specified AESIs is provided in Appendix 4.

PFIZER CONFIDENTIAL
Page 30

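### The AESI term list in SAP Appendix 4 has no thyroid diagnosis, no low-T4 term, no blood-pressure reading and no low-platelet term, so the AESI summary may be incomplete

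*SAP*

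**What the plan says.** Protocol Section 8.3.8 sets the categories: "AESIs include hemodynamic events, inflammatory events, and thyroid-related events". It lists no terms. SAP Section 6.6.1 supplies them by reference: "A list of pre-specified AESIs is provided in Appendix 4". Appendix 4 is therefore the only place where a category becomes something that can be programmed.

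The thyroid row of Appendix 4 is "Blood thyroid stimulating hormone abnormal;Blood thyroid stimulating hormone increased;Thyroxine free abnormal", ending with "Thyroxine increased".

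The risks behind the categories are in protocol Sections 2.2.1 and 2.3.1. For thyroid, the risk is raised TSH. For hemodynamics, the nonclinical finding is "minor and transient hemodynamic changes (increased blood pressure and decreased heart rate) at the high dose in cynomolgus monkeys". For inflammation and coagulation, it is a rise in fibrinogen together with "changes in platelets, globulin and albumin/globulin ratio and coagulation system (increase in PT and aPTT) in 14-day rat toxicology study".

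Protocol Section 10.3.3 tells sites how to name an event: "Whenever possible, the diagnosis (not the individual signs/symptoms) will be documented as the AE or SAE".

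**The concern.** A term list decides what is counted. If sites follow the protocol's naming preference and the event falls outside the list, the AESI summary does not show it. The thyroid row looks most exposed. It lists the isolated laboratory finding and a raised thyroxine, but not the low T4 or the underactive-thyroid diagnosis that a clinically important TSH rise would point to. The row contains no standardised MedDRA query (SMQ) that might bring those terms in.

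Blood pressure and platelets show a similar pattern. At stake is whether the AESI summary covers the three risk categories that the sponsor singled out for this compound.

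**Working it through.** No sample size, power or error rate is involved, so the check is a count of terms and a comparison of passages.

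**Step 1. Count the terms in SAP Appendix 4.**

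- Hemodynamic: 2 SMQs + 9 single terms = 11
- Inflammatory: 31
- Thyroid: 4
- Terms for a decrease: 2 of 11 hemodynamic (both heart rate), 0 of 31 inflammatory, 0 of 4 thyroid
- Thyroid diagnoses: 0 of 4
- Single terms naming a blood-pressure reading: 0 of 9

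**Step 2. Set each risk in the protocol beside the list.**

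| Risk in the protocol | Listed in Appendix 4 | Not listed |
|---|---|---|
| TSH raised | TSH increased, TSH abnormal | Thyroid diagnoses; thyroxine decreased; free thyroxine decreased or increased |
| Heart rate lowered | Heart rate decreased, bradycardia | None found |
| Blood pressure raised | Hypertension (and hypotension) | Blood pressure increased or decreased as a reading |
| Fibrinogen raised | Fibrinogen increased, hyperfibrinogenaemia | None found |
| PT and aPTT raised | Both prolonged | None found |
| Platelets changed, no direction given | Abnormal, increased, thrombocytosis | Platelet count decreased, thrombocytopenia |
| Albumin and total protein (monitored for the same risk) | Abnormal only | Either direction |

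**Step 3. Trace some recordings through the list.**

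- Raised TSH recorded as such: matches. In Phase 1 (protocol Section 2.2.2), 3 participants had raised TSH with free T4 in range and no related symptoms. Coded as TSH increased, 3 of 3 would be captured.
- Hypothyroidism: matches 0 of 4 thyroid terms.
- Low free T4 coded as a decrease: matches 0 of 4. It is caught only if coded as abnormal. Protocol Appendix 2 schedules free T4, so this is the form in which a low T4 would arise.
- Blood pressure increased: matches none of the 9 single terms. Whether an arrhythmia SMQ would catch it cannot be checked, because SMQ contents are not in the documents.
- Low platelet count coded as a decrease, or thrombocytopenia: matches 0 of 31.

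**Step 4. See where these events still appear.** SAP Section 6.2.2 tabulates all treatment-emergent AEs by system organ class and preferred term. Section 6.6.2 plans shift tables that include TSH, free T4, platelets, albumin and total protein. Section 6.6.3 summarises vital signs by arm. None of these feeds back into an AESI count.

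**The case against.** The strongest reply is that the list covers the main signals. TSH increased, fibrinogen increased, PT and aPTT prolonged, heart rate decreased and hypertension are all there. Nothing recorded as an AE is lost from the report, because the preferred-term tables and shift tables remain. This stands, and it confines the point to the AESI summary.

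Second, Section 10.3.3 prefers a diagnosis over signs and symptoms, while Section 10.3.1 separately requires an abnormal laboratory result to be recorded as an AE when it has accompanying symptoms or needs further testing or treatment. A relevant TSH rise could thus enter under a listed term even where a diagnosis is also made. By the same naming rule, a relevant blood-pressure rise would often be recorded as hypertension, which is listed. Both points stand. They make the gaps conditional on how a site records the event, but they do not close them.

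Third, upward terms suit a row headed inflammatory events, so leaving out low platelets could be deliberate. That is possible, but the protocol's platelet risk has no direction and the SAP gives no reason for the restriction.

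Two stronger readings are tempting, and the documents support neither.

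- A reader might size the undercount from the 3 TSH rises among 31 Phase 1 participants. The 31 include placebo, the 3 are reported across treatment groups, and the finding is itself a listed term. The figure says nothing about omitted terms.
- A reader might infer from protocol Section 8.2.6 ("Clinically significant abnormal laboratory findings are those which are not associated with the underlying disease") that raised CRP, fibrinogen or D-dimer will never become AEs in COVID-19. That sentence goes on to except values that the investigator judges more severe than expected. It also concerns the AE definition, which a change to Appendix 4 would not alter.

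**Conclusion.** The gap is real but narrow. Followed exactly, Appendix 4 leaves out of the AESI summary a thyroid diagnosis, a T4 or free T4 coded as decreased, and a platelet count coded as decreased. It also leaves out a blood-pressure reading, unless an SMQ supplies one. Albumin and total protein are caught only when coded as abnormal.

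The documents support saying that the summary may be incomplete, not that it will undercount. That depends on such events occurring and on sites or coders using unlisted terms, and the documents give a rate for neither. No size can be computed. The conclusion rests on the AESI summary being built from Appendix 4 alone, as SAP Section 6.6.1 implies. It does not bear on the primary result or on the completeness of overall AE reporting.

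**What to change.** Before unblinding, add to Appendix 4, with term names checked against the MedDRA version cited there:

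- hypothyroidism and hyperthyroidism diagnosis terms;
- thyroxine decreased, free thyroxine decreased and free thyroxine increased;
- blood pressure increased and decreased;
- platelet count decreased and thrombocytopenia;
- increased and decreased terms for albumin and total protein.

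Where the sponsor prefers to keep a restriction, state the reason in the appendix. If unblinding has already occurred, keep the present list and report the broader one as a labelled supplementary table. Separate counts from measured laboratory values are largely unnecessary, because the shift tables in SAP Section 6.6.2 already cover most of that ground.

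The cost is a revised term list and one re-run table from data already collected. The downside is that AESI counts may rise in both arms.

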Appendix 5. COVID-19 Signs/Symptoms
